Comparative Effectiveness Trial of Perioperative Telemonitoring for Functional Recovery and Symptoms
Brief Protocol Title for the Lay Public (if applicable):
NA
Study Phase:
Phase III Interventional
Participating Sites:
COH Duarte, COH South Pasadena, COH Antelope Valley, and COH Upland.
Rationale for this Study:
Patients experience a decrease in functional capacity following their surgery with an increase in symptoms, resulting in a dramatic decline in their quality of life (QOL). In addition to these challenges, patient's postoperative care and recovery primarily takes place in home settings due to increasing pressures to reduce readmissions and earlier postoperative discharge by the health care systems. As a result, physical function can decline severely and symptoms can progress before the surgical team is notified.
Objectives:
The primary purpose of this study is to test the efficacy of remote perioperative telemonitoring for functional recovery and postoperative complications in 438 GI, GU, GYN cancer surgery patients (398 patients for main trial, 40 for focus groups), comparing remote perioperative telemonitoring and surgeon care only patients.
Study Design:
This is a prospective, randomized, mixed methods, comparative effectiveness trial (1:1 randomization) of perioperative telemonitoring in cancer surgery (GI, GU, GYN). We plan to enroll 438 subjects (398 patients for the main trial, 40 for focus groups) over an approximate 40 months. This study will utilize the TapCloud™ application to conduct study procedures. Patients enrolled in the study will use the TapCloud™ application to capture subjective ePROs (symptoms). Patients will also be given an Actigraph GT9X Link, a research-grade accelerometer, to capture and report functional activity data (daily steps and sedentary time) throughout the duration of the study to the TapCloud™ application. The remote perioperative telemonitoring program consists of a real-time, alert/feedback system that will trigger alerts into the TapCloud™ application when pre-determined thresholds are exceeded. Clinical RNs will respond by initiating contact using the TapCloud™ application's secure messaging system, or telephone calls if unsuccessful, to assess, triage, manage, and resolve the issue.
Endpoints:
Primary:

Higher daily steps, lower postop complications Secondary: Sleep, sedentary time, symptom severity, symptom interference, readmissions
Sample Size:
438 Patients (398 patients for the main trial, 40 for focus groups)
Estimated Duration of the Study
40 months
Summary of Subject Eligibility Criteria:
Study eligibility criteria include: 
 • Cancer patients scheduled to undergo major abdominal surgery for GI, GU, or GYN malignancies or presumed GI, GU, or GYN malignancies (as determined by surgeons); • Ability to read and understand English or Spanish, and • Age 18 years or older
Investigational Product Dosage and Administration:
NA
Clinical Observations and Tests to be Performed:
Diagnosis, tumor stage, neoadjuvant treatments, Charlson-Deyo co-morbidity index, time to adjuvant treatment, pre-op Zubrod/ECOG performance score, name of procedure, open or minimally invasive, ASA classification, date of surgery, post-op admission status and date, ICU days, post-operative events, discharge date, discharge status, preop objective functional measures (6-Minute Walking Test, Timed Up and Go, Short Physical Performance Battery).
Statistical Considerations:

Aim 1 - The Aim's primary endpoint will be the percent change from preoperative baseline in daily step count during the first 2 weeks post-discharge from hospital (measured on Discharge Day, Day +7, and Day +14). To recognize that these data may be missing not at random (ie, due to adverse event, distress, or withdrawal of consent), the effect of study intervention on primary endpoint will be modeled jointly with early withdrawal from data collection of that endpoint. Within the joint model, the sub-model for the primary endpoint will use generalized linear mixed modeling (with treatment and covariates as fixed factors, patient ID as random factor), while the other sub-model will analyze time to early withdrawal (Aim 3's primary endpoint) using proportional hazards regression. Similar joint modeling will be carried out for Aim 1's secondary endpoints (change from baseline in sedentary time, general symptoms, disease-specific symptoms).
 
Aim 2 - The Aim's primary endpoint will be maximum Comprehensive Complications Index (CCI) during the 30 days post-discharge. Maximum CCI will be categorized as above vs below 15, and logistic regression will be used to evaluate the effect of study intervention. The Aim's secondary endpoint, time to hospital readmission through 90 days, will be subjected to survival analysis, handling any early withdrawal from study as a competing endpoint.

Aim 3 - Treatment will be evaluated for association with this Aim's primary endpoint, time to early withdrawal, using proportional hazards regression. This analysis will be generated as a sub-model of the joint modeling for Aim 1.

Aim 4 - Qualitative data from open-ended exit surveys and focus groups will be analyzed using the conventional content analysis approach.⁷³ For focus groups, participants can choose to attend by telephone, videoconferencing, or in-person. This approach is used to describe a phenomenon where existing theory or research literature is limited. Data will be transcribed and analyzed using HyperRESEARCH™ qualitative software. Transcripts will be imported allowing for the development of analytic categories, data coding, and review of coded data. All data will be read repeatedly to achieve immersion and obtain a sense of the whole. Then, data will be read to derive codes, and sorted into themes based on links and relationship. [name] and [name] will conduct a final validation review of the codes/themes to ensure consistency and clarity across all qualitative data. Data discordantly coded will be discussed for refinement and consensus purposes with the SAC.

Sponsor/Licensee:

Patient-Centered Outcomes Research Institute

Case Report Forms

Not Applicable

Table of Contents

SECTION	PAGE
1.0 Goals and Objectives (Scientific Aims).....	10
2.0 Background.....	11
2.1 Introduction/Rationale for Development	11
2.2 Overview of Proposed Study	12
2.3 Preclinical Studies.....	12
2.4 Human Studies.....	12
3.0 Patient Eligibility	13
3.1 Inclusion Criteria	13
3.1.1 Disease Status	14
3.1.2 Age Criteria, Performance Status and Life Expectancy	14
3.1.3 Child Bearing Potential.....	14
3.1.4 Protocol-Specific Criteria	14
3.1.5 Informed Consent/Assent	14
3.1.6 Prior Therapy	14
3.2 Exclusion Criteria	14
3.2.1 Study-Specific Exclusions	14
3.2.2 Non-Compliance.....	14
3.3 Inclusion of Women and Minorities	14
4.0 Screening and Registration Procedures.....	14
4.1 Screening Procedures.....	14
4.2 Informed Consent	15
4.3 Registration Requirements/Process	15
4.4 Randomization and/or Dose Level Assignment.....	15
5.0 Treatment Program	15
5.1 Program Overview – Conceptual Framework	15
5.2 Planned Duration of Therapy.....	21
5.3 Criteria for Removal from Treatment	21
5.4 Subject Follow-Up.....	21
5.5 Supportive Care, Other Concomitant Therapy, Prohibited Medications	21
5.6 Additional Studies.....	22
5.6.1 Laboratory Studies.....	22

1.0 Goals and Objectives (Scientific Aims)

The most common and effective treatment for cancer is surgery. By definition, surgical procedures are invasive; patients experience an abrupt decline in functional capacity after surgery. In addition to postoperative functional declines, patients experience an increase in symptoms, such as pain, fatigue, and distress.¹⁻³ Postoperatively, these symptoms contribute to a dramatic decline in quality of life (QOL).⁴⁻⁶ Postoperative recovery challenges are compounded by healthcare systems-related trends, including pressures to reduce readmissions and earlier postoperative discharge. As a result, the majority of postoperative care and recovery takes place at home. After hospital discharge, physical function can decline severely and symptoms can progress before the surgical team is notified.

A promising approach to early identification of post-discharge complications is through remote, real-time perioperative telemonitoring of functional activity and patient-reported outcomes (PROs). The approach can identify patients at risk for post-discharge complications, treat symptoms/complications in a real-time fashion, and prevent readmissions. The overall purpose of this study is to conduct a multi-site, comparative effectiveness, randomized controlled trial of perioperative telemonitoring for functional recovery in 438 English and Spanish-speaking cancer patients (398 for the main trial, 40 for the focus groups) scheduled to undergo major abdominal surgery (GI, GU, GYN). The program will be implemented at three geographically diverse sites in the Greater Los Angeles area, including one serving a low resource, socioeconomically-disadvantaged population. Accordingly, we propose the following specific aims:

Aim 1: Compare the impact of remote perioperative telemonitoring care versus surgeon only perioperative care on clinically significant changes in functional recovery (accelerometer daily step count) and related secondary patient-centered outcomes (sleep, sedentary time, symptom severity, symptom interference with daily activities).

Hypothesis: Remote perioperative telemonitoring improves functional recovery after major abdominal surgery.

Aim 2: Compare the impact of remote perioperative telemonitoring care versus surgeon only perioperative care on postoperative complications (Comprehensive Complications Index – CCI) and related secondary surgical outcomes (hospital readmission).

Hypothesis: Remote perioperative telemonitoring reduces postoperative complications in the 30 days after major abdominal cancer surgery.

Aim 3: Compare early withdrawal (dropout or loss of accelerometer device) between the comparators.

Hypothesis: Remote perioperative telemonitoring does not excessively burden patients and families.

Aim 4: Explore perioperative telemonitoring care-related experiences (acceptability, technology usability, uptake/integration) among patients, families, and surgeons/nurses through qualitative focus groups and open-ended exit surveys.

Research Question: What are the various stakeholder's perspectives on remote perioperative telemonitoring care?

2.0 Background

2.1 Introduction/Rationale for Development

Surgical Oncology is Increasingly Focused on Quality, Value, and Patient-Centeredness. Surgeons and cancer centers are increasingly asked to provide evidence of the quality and value of their care. Historically, surgical outcomes are measured by disease- and systems-related parameters, such as length of hospital stay, morbidity, readmission rates, and mortality.^{16, 17} While important, these measures do not accurately reflect the surgical care experience from a patient's perspective. Patient-centered outcomes are increasingly being used in routine cancer care as quality and value indicators.¹⁷⁻¹⁹ However, these outcomes are not adequately understood and routinely integrated into surgical oncology.

Cancer Surgery is Complex, and Post-Operative Functional Impairments and Symptom Burden Are Common. More than 45 million Americans undergo surgery each year.²⁰ Greater than 60% of cancer patients undergo surgical interventions²¹, and surgical interventions account for the most cures after a cancer diagnosis.²² Patients who undergo cancer surgery experience functional deficits and symptoms that negatively affect their recovery activities.²³ Post-op functional impairments are common, including inability to perform activities of daily living.²⁴ Postoperative physical function is predictive of complications such as thromboembolism, pneumonia, and sarcopenia, resulting in prolonged hospital stays and readmissions.^{2, 25-30} Fatigue and pain are common, occurs in 80% of patients, and persists one year after surgery.^{22, 31} Other common symptoms include sleep disturbance, anxiety, depression, and loss of appetite.^{1, 24}

Monitoring Postoperative Recovery from Cancer Surgery is Challenging after Discharge. Due to changes in healthcare and advances in surgical techniques, surgeons are asked to discharge patients earlier after surgery. Operations that were previously associated with 10-20 day hospital stays are now outpatient or short-stay procedures. Postoperative complications that traditionally arise in the hospital are also developing in the community and at home. The current delivery model for post-discharge care is largely inefficient and not proactive.³² Home health nurses are often dispatched for unresolved acute problems. Patients may contact the hospital when acute problems arise, but are often unaware of when to contact their surgeons (RQ-3). This often requires hours or days to resolve, and is burdensome for patients, families, and the healthcare system. Delays in communicating critical conditions may escalate problems beyond outpatient care. In critical situations, emergency room visits within the same healthcare system or at a different institution occur, resulting in inefficient and fragmented care.

The burden of postoperative hospital readmissions after major cancer surgery is high.³³⁻³⁵ Depending on the tumor site, 90-day readmission rates for major cancer surgery range from 23-43%.³⁶ Published data suggest that 30- and 90-day readmission rates are 30% and 43% for cystectomy, and 22% and 35% for esophagectomy and pancreatectomy.^{36, 37} Hospital readmissions are burdensome, and result in higher 1-year mortality rates, and delays in timing and eligibility for adjuvant therapies.³³ Predictors of readmissions are similar across different tumor sites, and include functional impairments, comorbid conditions, and postoperative complications.^{36, 38}

There are Critical Knowledge Gaps on the Impact of Patient-Centered Outcomes in Cancer Surgery. The impact of routine symptom monitoring is predominantly tested in chemotherapy settings.^{39,40} These findings suggest a positive effect on patient-provider communication⁴¹⁻⁴⁴, detection of unrecognized problems^{40, 44-47}, guiding clinical care^{46, 48-50}, health outcomes⁵⁰⁻⁵⁴, and survival.⁹ Few studies are conducted in surgical oncology, and few

included assessments/support before surgery.²⁹ Current evidence suggest that functional activity is correlated with surgical outcomes. Higher Fitbit step counts in elderly patients after cardiac surgery was correlated with early recovery, shorter hospital stay, and more discharge to home.²⁷ Other recent studies include real-time location systems to promote early mobilization after abdominal surgery⁵⁵, Fitbit step counts during inpatient recovery from metastatic cancer surgery (predictive of risk for 30 and 60 day readmission)⁵⁶, feasibility and validity of accelerometer-based physical activity data for postoperative recovery⁵⁷, and mobile application and web-based PROs after major GI and gynecologic surgery.^{8, 11}

Although these data are promising, critical knowledge gaps exist. First, the empirical evidence in combining subjective and objective real-time health-related data is lacking.^{32, 58} Current ongoing trials, including those funded through PCORI, are designed to focus primarily on post-operative symptoms. Second, current and prior studies did not assess outcomes at baseline (before surgery). This is important because evidence suggests that preoperative functional activity and PROs can predict the trajectory of functional and symptom recovery after surgery.¹

Despite the documented evidence and commercial availability of patient digital engagement platforms, the question remains whether telemonitoring is equally as beneficial or more beneficial for patients and families as standard surgeon only care. Both comparators have demonstrated benefits. It is possible that telemonitoring could provide more proactive, real-time quality surgical care earlier in the treatment course, however, clinical trials have not yet compared telemonitoring surgical care with surgeon only care. In addition, despite the evidence on the benefits of telehealth in oncology care, there is a lack of consensus on how best to integrate this into surgical care. Both comparators in this study are available to patients now; however, there is a need to compare both models and generate a stronger evidence base for patient-centered surgical care to inform clinical practice and policies

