13.2 Statistical Analysis Plan

Data Management - We expect a total of 12 symptom evaluations per participant over the 3-4 month study duration. With a total sample of 332, this yields approximately 4,000 data collection encounters overall. We expect a large number of daily steps data observations per subject, as functional recovery data will be continuously recorded on a daily basis over the study duration.

Data will be transferred in real-time (within 2 minutes of participant completion) from TapCloud™ to a REDCap (Research Electronic Data Capture) study database. Daily step count will be continuously transferred to the study database in real-time. The database resides in secure COH research networks for research team access only. An assigned master's-level Statistical Research Associate (SRA) with paid effort on the project will be responsible for coordinating monthly data transfer, auditing, and data cleaning. In the process of data transfer and mergers, the study biostatistician ([name]), SRA, and TapCloud™ representative will audit and clean the data, apply formats in statistical software, and export data into REDCap database.

Handling Missing Data and Lost to Follow-Up - We will integrate the following strategies to prevent, detect, and remedy missing data in real time. First, participants will receive a total remuneration of \$50 for providing data. Second, research staff will provide telephone/email reminders before each of the scheduled data collection timepoints to maximize adherence. Regular contact will also be provided to remind participants to wear the accelerometer. Third, research staff will provide each participant with a simple study calendar with data collection dates. Fourth, if no data is completed by participants, research staff will contact the participant in real-time to engage and assess. The Statistical Methods section below describes how data missing not at random will be handled in the analyses.

Preliminary Analysis - Descriptive statistics will be used to summarize all variables. Characteristics of participants at baseline will be reported in tabular form using appropriate descriptive statistics. Prior to hypothesis testing, the relationship between demographic variables and primary outcome variables (daily step count, postop complications) will be examined. Significant relationships/correlations will guide the addition of demographic variables to the analysis.

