Heterogeneity of Treatment Effect - Exploratory use of interaction terms will assess whether significant effects of the study intervention differ by sex or by age (i.e., above vs below 70 years). If found to be present, any such heterogeneity of treatment effect, not having been hypothesized in advance, will be reported as a preliminary finding that awaits confirmation in future studies.

Internal/External Validity and Avoidance of Bias - To limit possible confounding of the primary results, analyses of the prespecified hypotheses will be adjusted for covariates (age, sex, physical fitness at pre-surgical baseline). To assess the representativeness of study participants, their demographic characteristics (sex, age) will be compared to those of eligible patients who are approached for consent but decline to participate in the study. Our digital engagement platform will initiate reminder systems to reduce loss to follow-up.

Statistical Methods by Study Aims - Characteristics considered as potential covariates in all analyses will be age, sex, surgical technique, residential setting, and physical fitness at preoperative baseline. Any covariate that improves the model's fit to the observed data will be retained in the final analysis.

The analyses for Aims 1-3 will be by intention to treat (ITT); the ITT population will include all subjects who have given informed consent, been randomized to intervention or control arm, and undergone the planned cancer surgery.

Aim 1 – Allowing for an anticipated 20% attrition in use of accelerometer by Day 14 across both trial arms, an initial sample size of 332 (randomized 1:1) will provide (per East 6.5 software)

80% power to detect the hypothesized 14% difference in slope due to study intervention, using a 1-sided, repeated measures-difference of slope test with alpha=0.025.

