The Aim's primary endpoint will be the percent change from preoperative baseline in daily step count during the first 2 weeks post-discharge from hospital (measured on Discharge Day, Day +7, and Day +14). percent change from preoperative baseline in daily step count during the first 2 weeks post-discharge from hospital (measured on Discharge Day, Day +7, and Day +14). To recognize that these data may be missing not at random (ie, due to adverse event, distress, or withdrawal of consent), the effect of study intervention on primary endpoint will be modeled jointly with early withdrawal from data collection of that endpoint. Within the joint model, the sub-model for the primary endpoint will use generalized linear mixed modeling (with treatment and covariates as fixed factors, patient ID as random factor), while the other sub-model will analyze time to early withdrawal (Aim 3's primary endpoint) using proportional hazards regression. Similar joint modeling will be carried out for Aim 1's secondary endpoints (change from baseline in sedentary time, general symptoms, disease-specific symptoms).

Aim 2 – Because the CCI is derived from data routinely entered in the medical chart, no loss to follow-up is anticipated for this endpoint. A sample size of 332 subjects randomized 1:1 will provide (per East 6.5 software) 88% power to detect the hypothesized CCI benefit, using a 1-sided test of proportions, unpooled estimate of variance, critical p-value for efficacy=0.024, cumulative alpha=0.025.

The Aim's primary endpoint will be maximum Comprehensive Complications Index (CCI) during the 30 days post-discharge. Maximum CCI will be categorized as above vs below 15, and logistic regression will be used to evaluate the effect of study intervention. The Aim's secondary endpoint, time to hospital readmission through 90 days, will be subjected to survival analysis, handling any early withdrawal from study as a competing endpoint.

Aim 3 - The trial's sample size of n=332 will provide (per SAS software, PROC POWER for two-sample comparison of proportions) at least 80% power.

Treatment will be evaluated for association with this Aim's primary endpoint, time to early withdrawal, using proportional hazards regression. This analysis will be generated as a sub-model of the joint modeling for Aim 1.

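### Comorbidity is collected and named as a predictor of readmission, but the covariate rules leave it out of the 90-day readmission model: a modest, avoidable loss of efficiency

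*Combined protocol and SAP*

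**What the plan says.** Four places bear on this.

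- **Section 2.1** gives the predictors of readmission: "Predictors of readmissions are similar across different tumor sites, and include functional impairments, comorbid conditions, and postoperative complications". Time to readmission through 90 days is the secondary endpoint of Aim 2.
- **Synopsis, Clinical Observations and Tests to be Performed** lists the data to be gathered, beginning "Diagnosis, tumor stage, neoadjuvant treatments, Charlson-Deyo co-morbidity index, time to adjuvant treatment". As printed, neither section 12.1.3 nor the study calendar mentions the index, so its scoring date is not stated.
- **Section 13.2, Statistical Methods by Study Aims** sets the candidates: "Characteristics considered as potential covariates in all analyses will be age, sex, surgical technique, residential setting, and physical fitness at preoperative baseline". It then adds: "Any covariate that improves the model's fit to the observed data will be retained in the final analysis". A shorter list appears just above, under Internal/External Validity: "analyses of the prespecified hypotheses will be adjusted for covariates (age, sex, physical fitness at pre-surgical baseline").
- **Section 13.2, Preliminary Analysis** gives the one route for further covariates: "Significant relationships/correlations will guide the addition of demographic variables to the analysis".

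The Aim 2 power statement reads: "A sample size of 332 subjects randomized 1:1 will provide (per East 6.5 software) 88% power to detect the hypothesized CCI benefit". It refers to a one-sided test of proportions with no covariates. No power is stated for readmission.

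**The concern.** Section 2.1 names three kinds of predictor. Functional impairment is represented among the candidates by preoperative fitness. Postoperative complications arise after assignment and should not be adjusted for. Comorbidity is the only usable baseline predictor left, and it is on neither list. It is not a demographic variable, so the Preliminary Analysis route does not admit it. The documents give no reason for leaving it out.

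What is at stake is precision. In a hazard or logistic model, leaving out a baseline variable that predicts the outcome lowers the power of the treatment test, by an amount that depends on how strongly it predicts. There is also a prespecification cost: if the readmission result is close, adding comorbidity after the data are seen would look post hoc.

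**Working it through.** **1. The plan's own figure.** The 88% cannot be reproduced, because neither the rates of CCI above 15 nor the hypothesised benefit is given. It can be back-solved. With 166 per arm, unpooled variance and one-sided p of 0.024:

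power = Φ( (p_c − p_t) / √[p_c(1−p_c)/166 + p_t(1−p_t)/166] − z_0.976 )

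For p_c = 0.30 and p_t = 0.157, the difference is 0.143, the standard error is √(0.00127 + 0.00080) = 0.0454, the ratio is 3.15, and Φ(3.15 − 1.98) = 0.88. Other pairs that give 88% are 20% v 8.1%, 40% v 24.1% and 50% v 33.2%. The figure is therefore attainable, and no covariate enters it.

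**2. Readmission.** From the documents: 90-day rates of 23–43% (section 2.1), 166 per arm, analysis by survival methods. Assumed: control rates of 23%, 33% (the midpoint) and 43%; a 40% relative reduction; one-sided 0.025; a standard-normal comorbidity score x with hazard ∝ exp(β·treatment + γx), where γ = ln(HR per SD); censoring at 90 days only. Marginal rates were held fixed as γ varied. Power of Cox regression without and with x, 6,000 trials per cell, no other covariates:

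| Control rate | HR 1.25 per SD | HR 1.5 per SD | HR 2.0 per SD |
|---|---|---|---|
| 23% | +0.6 points | 58.5% → 59.5% (+1.0) | 58.1% → 62.5% (+4.4) |
| 33% | +0.5 | 78.4% → 79.6% (+1.3) | 77.6% → 83.4% (+5.8) |
| 43% | +0.3 | 91.7% → 93.3% (+1.6) | 92.3% → 95.9% (+3.6) |

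A second calculation (35% control rate, conditional treatment HR 0.55, about 93 events, 2,500 trials) gave 79% → 79.5% at HR 1.5 and 75% → 81% at HR 2.0. Together: about 0.5 to 1.6 points at HR 1.5 and about 4 to 6 at HR 2.0. With a score that predicts nothing (HR 1.0), adjustment changed power by less than 0.1 point.

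**3. Complications (maximum CCI above v below 15).** Logistic regression at the back-solved rates, one-sided 0.024:

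| Comparison model | OR 1.5 per SD | OR 2.0 per SD |
|---|---|---|
| No other covariates (control rate 20–50%) | +0.6 to +1.1 points | +1.4 to +2.8 |
| One covariate already in, correlation 0.3 or 0.5 with comorbidity | +0.1 to +0.6 | +1.5 to +1.9 |
| One covariate already in, correlation 0.4 | +0.5 to +0.7 | +1.7 to +2.0 |

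The covariate already in the model was given an OR of about 1.5 per SD. In the second row the comorbidity OR is before adjustment for it; in the third it is conditional on it. Rows two and three use control rates of 30% and 40%. They are the relevant ones, because the plan already offers age and fitness. Together they give 0.1 to 0.7 points at OR 1.5 and 1.5 to 2.0 at OR 2.0.

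**4. Chance imbalance.** The 95% range for the between-arm difference in a baseline score is ±1.96 × √(2/166) = ±0.22 SD. That moves the log odds ratio by about ±0.22 × ln 1.5 = ±0.09, or ±0.22 × ln 2.0 = ±0.15. At 30% v 15.7% the treatment effect is a log odds ratio of 0.83 in size. The unadjusted test already allows for this variation; adjustment removes it.

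**The case against.** The case against acting has real force.

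- **Endpoint.** Section 2.1 links comorbidity to readmission only. For complications the documents point to physical function and to step counts (section 2.4), and nowhere say that comorbidity predicts the CCI. This stands: the CCI part is an inference.
- **Comparator.** The readmission figures set a model with comorbidity against one with no covariates, whereas the plan already offers five candidates. This stands too. The CCI runs show that overlap trims the gain without removing it; no matching run was made for readmission, so those figures are at the upper end.
- **Judgement.** Stage, neoadjuvant treatment and performance score are also collected, and one could argue for each. But comorbidity is the one that the protocol itself names as a predictor of readmission.
- **Wording.** "Any covariate that improves the model's fit to the observed data will be retained in the final analysis" could be read as open to any variable. It follows directly on the candidate list, so the natural reading is any covariate from that list. On the open reading, comorbidity would enter only by a data-driven choice, which is not prespecification.

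Three stronger conclusions are tempting, and the documents support none of them. A reader might infer that the 88% is overstated; it is for an unadjusted test and claims no gain from covariates. A reader might infer that the omission biases the treatment comparison; randomisation protects against systematic bias, and the smaller odds or hazard ratio from a model with fewer covariates is a different, less conditional estimand with a valid test. A reader might infer a material loss of power for the primary complications endpoint, or a need for more patients; that requires a strong predictor, a link to the CCI that the documents do not state, and a comparison that ignores the covariates already offered.

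**Conclusion.** The point holds as a free improvement. Followed as written, section 13.2 leaves out of the 90-day readmission model a baseline variable that the trial collects and that the protocol names as a predictor of that outcome. The cost is some efficiency. Validity, type I error and the stated power are untouched.

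Its size cannot be derived from the documents. For readmission it is about a point at moderate assumed strength and reaches 4 to 6 points only if comorbidity is a strong predictor. Those figures also rest on an assumed treatment effect and ignore the competing-event handling of early withdrawal. For the CCI, at most about 2 points are in play up to an odds ratio of 2.0 per SD. The reason to act is that the change is nearly free, more than that the gain is large.

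**What to change.** In section 13.2, under Aim 2, state that the "Charlson-Deyo co-morbidity index", scored from conditions present before randomisation, is a prespecified covariate in the 90-day readmission model and is kept whether or not it improves fit. As a reasonable extension, state the same for the CCI logistic model. Say when and from what source the index is scored, so that no condition arising after assignment enters it. In the same edit, reconcile the two covariate lists in 13.2, so that it is clear which one governs Aim 2. Make the change before outcome data are seen by arm.

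The cost is a sentence or two of SAP text and one degree of freedom per model. It needs no further patients, procedures or data items.
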